9.3 POPULATIONS FOR ANALYSES

We will use an Intention-to-Treat (ITT) Analysis Dataset, including all randomized participants (either to transdermal estradiol patch and micronized progesterone pill, or placebo patch and placebo pill).

9.4 STATISTICAL ANALYSES

9.4.1 GENERAL APPROACH

Descriptive statistics of continuous data will be presented as adjusted means (least squared means) and standard errors. A two-tailed p-value of $\leq .05$ will be considered as statistical significance.

Examinations of residual normality, linearity, homogeneity of variance, and influential outliers will be performed using the SAS Macro Mixed DX¹⁷⁶. Outliers at 2 SD's or more above or below the mean will be winsorized. For cortisol, the distribution of the values before and after every Trier Social Stress Test will be visually inspected and, in the case of skewness, a log-transformation will be performed.

We will use two-way repeated measures analyses with between-subject factors. Our models will test whether there is a mean value change in the primary and secondary outcomes from week 8 to weeks 16, 20, and 24 (within-subject analyses) and based on the treatment arm (between-subject analyses of transdermal estradiol vs. placebo treatment groups). We expect a significant change over time in the primary and secondary outcome measures in those randomized to active transdermal estradiol, but not in those randomized to placebo. Data will be analyzed using proc mixed in SAS. All models will use an auto-regressive covariance structure to account for the repeated assessments of primary and secondary outcomes in the same participants.

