1 PROTOCOL SUMMARY

1.1 SYNOPSIS

Title:	The Menopause Transition: Estrogen Variability, HPA axis and Affective Symptoms
Study Description:	Women in the menopause transition ('perimenopause') are exposed to extreme hormone variability, tend to experience a unique set of severe stressors (e.g., divorce, death of loved ones), and are also at substantially elevated risk to suffer from mood and anxiety disorders. The purpose of this research is to understand the mechanisms by which variability in estradiol (E2) is associated with the symptoms of anxiety and anhedonia (loss of interest and pleasure - a common symptom of depression). By stabilizing E2 variability with a hormonal manipulation, this research will determine the degree to which the E2 variability (or E2 levels) plays a causal role in perimenopausal anxiety and anhedonia symptoms and whether it does so by affecting biological responses to stress.
Objectives:	
Primary Objectives:
 
1. Change over time in anxiety score from State-Trait Anxiety Inventory [Time Frame: Baseline (Week 8), Weeks 16, 20 and 24]2. Change over time in anhedonia score from the Snaith-Hamilton Pleasure Scale [Time Frame: Baseline (Week 8), Weeks 16, 20 and 24] 
Secondary Objectives:
 
1. Change over time in AUC cortisol stress response [Time Frame: Baseline (Week 8), Weeks 16, 20 and 24]2. Change over time in threat reactivity from Dot Probe behavioral task [Time Frame: Baseline (Week 8), Weeks 16, 20 and 24]

3. Change over time in measure of effort for motivation and anhedonia from Effort Expenditure for Reward Task [Time Frame: Baseline (Week 8), Weeks 16, 20 and 24]

Endpoints:

Primary Endpoints:

1. Change in STAI score [Time Frame: Baseline (Week 8), Weeks 16, 20 and 24]
2. Change in SHAPS score [Time Frame: Baseline (Week 8), Weeks 16, 20 and 24]

Secondary Endpoints:

1. Change in AUC cortisol response [Time Frame: Baseline (Week 8), Weeks 16, 20 and 24]
2. Change in “threat bias” score from Dot Probe task [Time Frame: Baseline (Week 8), Weeks 16, 20 and 24]
3. Change in “hard choice” score from EEfRT [Time Frame: Baseline (Week 8), Weeks 16, 20 and 24]

Study Population:

250 medically healthy female volunteers aged 45-60 undergoing natural menopause transition who meet STRAW+10 criteria for early or late menopause transition and are candidates for transdermal E2 and have had a normal mammogram in the previous 12 months.

Phase:

N/A

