3 OBJECTIVES AND ENDPOINTS

OBJECTIVES	ENDPOINTS	JUSTIFICATION FOR ENDPOINTS
Primary		
The primary objective of this study is to use transdermal estradiol to determine the pathophysiologic role of estradiol in clinically significant symptoms of anxiety and anhedonia in the menopausal transition.	The primary endpoints are changes in mean levels from week 8 (baseline) to weeks 16, 20, and 24 in validated questionnaires for symptoms of anxiety and anhedonia. Specifically, the validated State-Trait Anxiety Inventory and the Snaith-Hamilton Pleasure Scale (SHAPS) will be assessed.	The goal is to establish whether there is a causal role of estradiol in the clinically relevant anxiety and anhedonia symptoms seen in perimenopausal women.
Secondary		
The secondary objectives of this study are to use transdermal estradiol to determine i) the role of	The secondary endpoints are changes from week 8 (baseline) to weeks 16, 20, and 24 in i) mean levels of	The goal is to establish whether there is a causal role of estradiol

OBJECTIVES	ENDPOINTS	JUSTIFICATION FOR ENDPOINTS
estradiol in anxiety and anhedonia related behaviors and ii) if HPA stress activation is a biomarker of estradiol-related behavior and symptomatology.	behavioral measures of anxiety (Dot Probe task) and anhedonia (EEfRT task) and ii) in serum cortisol stress-reactivity, as a marker of HPA stress activation	in the clinically relevant anxiety and anhedonia related behaviors and stress physiology in perimenopausal women.

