9.1 STATISTICAL HYPOTHESES

- Primary Efficacy Endpoint(s):
 - 1. Change in State-Trait Anxiety Inventory score [Time Frame: Baseline (Week 8), Weeks 16, 20 and 24]
 - H0: The mean scores of the State-Trait Anxiety Inventory are the same at baseline (week 8), and weeks 16, 20, and 24, both, in those randomized to active treatment and in those randomized to placebo.
 - H1: The mean scores of the State-Trait Anxiety Inventory will significantly change from baseline (week 8) to weeks 16, 20, and 24 in those randomized to active treatment, but not in those randomized to placebo.
 - 2. Change in SHAPS score [Time Frame: Baseline (Week 8), Weeks 16, 20 and 24]
 - H0: The mean scores of the SHAPS will not change from baseline (week 8) to weeks 16, 20, and 24, both, in those randomized to active treatment and in those randomized to placebo.
 - H1: The mean scores in the SHAPS score will significantly change from baseline (week 8) to weeks 16, 20, and 24 in those randomized to active treatment, but not in those randomized to placebo.
- Secondary Efficacy Endpoint(s):
 - 1. Change in AUC cortisol response [Time Frame: Baseline (Week 8), Weeks 16, 20 and 24]

- H0: The cortisol AUC will not change from baseline (week 8) to weeks 16, 20, and 24, both, in those randomized to active treatment and in those randomized to placebo.
- H1: The cortisol AUC will significantly change from baseline (week 8) to weeks 16, 20, and 24 in those randomized to active treatment, but not in those randomized to placebo.
- 2. Change in “threat bias” score from Dot Probe task [Time Frame: Baseline (Week 8), Weeks 16, 20 and 24]
 - H0: The mean score in the Dot Probe task will not change from baseline (week 8) to weeks 16, 20, and 24, both, in those randomized to active treatment and in those randomized to placebo.
 - H1: The mean score in the Dot Probe task will significantly change from baseline (week 8) to weeks 16, 20, and 24 in those randomized to active treatment, but not in those randomized to placebo.
- 3. Change in “hard choice” score from EEfRT [Time Frame: Baseline (Week 8), Weeks 16, 20 and 24]
 - H0: The mean score in the EEfRT task will not change from baseline (week 8) to weeks 16, 20, and 24, both, in those randomized to active treatment and in those randomized to placebo.
 - H1: The mean score in the EEfRT task will significantly change from baseline (week 8) to weeks 16, 20, and 24 in those randomized to active treatment, but not in those randomized to placebo.

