9.2 SAMPLE SIZE DETERMINATION

Sample size calculations were performed for the primary outcome measures. Correlation and effect size estimations were based on previously published literature ^{173,174}. With a sample size of N=120 and performing hypothesis tests at two-sided alpha=.05 and a correlation of >.25 among repeated measures, we have >90% power to detect a small effect size of .15.

The G*power software was used to determine the sample size ¹⁷⁵, based on a repeated measures ANOVA with within-between interaction ^{173,174}. We conservatively account for 15% (n =18) withdrawal following randomization, yielding 138 women who complete the protocol (powered for 120). This sample size will provide sufficient power to address secondary endpoints. No exploratory analyses will be performed.

By using proc mixed (not GLM), we will apply an analysis which is relatively robust to missing data. Before applying proc mixed, we will check for the randomness of missing data.

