9.4.2 ANALYSIS OF THE PRIMARY EFFICACY ENDPOINT(S)

For each primary endpoint:

1. Change in the Anxiety score from State-Trait Anxiety Inventory

State anxiety will be assessed using the validated State-Trait Anxiety Inventory. The State-Trait Anxiety Inventory consists of 20 questions on a 4-point force-choice Like-type response scale (scores 0 - 3). The 20 questions are summed together for a final score. The score can range from 0 to 60 with higher scores representing higher levels of anxiety. Continuous, interval scaled sum scores will be calculated and treated as a repeated measure (assessed at weeks 8, 16, 20, and 24). Change in State-Trait anxiety inventory will be analyzed using two-way repeated-measures analysis for a time and treatment effect (proc mixed in SAS). Models will use an auto-regressive covariance structure to account for the repeated assessments in the same participants. Outliers at 2 SD's or more above or below the mean will be winsorized. Missing data will not be imputed, as the statistical procedures we will apply (proc mixed) are robust to randomly distributed missing data. Before applying proc mixed, we will check for the randomness of missing data. Results of the statistical procedures will be presented as adjusted means (least squared means) with standard errors.

2. Change in anhedonia score from Snaith-Hamilton Pleasure Scale

Anhedonia will be assessed using the validated Snaith-Hamilton Pleasure Scale (SHAPS). Scores range from 0-14, with higher scores corresponding to higher levels of anhedonia. The questionnaire will be applied at weeks 8, 16, 20 and 24. Continuous, interval scaled sum scores will be calculated and treated as a repeated measure (assessed at weeks 8, 16, 20, and 24). Change in the SHAPS will be analyzed using two-way repeated-measures analysis for treatment x week (proc mixed in SAS). Models will use an auto-regressive covariance structure to account for the repeated assessments of primary and secondary outcomes in the same participants. Outliers at 2 SD's or more above or below the mean will be winsorized. Missing data will not be imputed, as the statistical procedures we will apply (proc mixed) are robust to randomly distributed missing data. Before applying proc mixed, we will check for the

randomness of missing data. Results of the statistical procedures will be presented as adjusted means (least squared means) with standard errors.

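### STAI and SHAPS are both primary, each tested at two-sided .05 with no multiplicity rule; if either can carry the Section 3 claim, the false-positive chance is about 7–10%.

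*Combined protocol and SAP*

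**What the plan says.** The synopsis (1.1) names two primary endpoints, "Change in STAI score [Time Frame: Baseline (Week 8), Weeks 16, 20 and 24"] and "Change in SHAPS score [Time Frame: Baseline (Week 8), Weeks 16, 20 and 24"], and numbers two primary objectives, one per scale. Section 3 instead has a single primary objective: "The primary objective of this study is to use transdermal estradiol to determine the pathophysiologic role of estradiol" in symptoms of both anxiety and anhedonia. Its stated goal is to establish whether estradiol plays a causal role in those symptoms.

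Section 9.1 gives each scale its own null and alternative hypothesis; for SHAPS the alternative begins "The mean scores in the SHAPS score will significantly change from baseline (week 8) to weeks 16, 20, and 24". Section 9.4.2 opens with "For each primary endpoint" and then describes one mixed model per scale. Section 9.4.1 sets a single threshold for everything: a two-tailed p of .05 or less "will be considered as statistical significance". The power calculation in 9.2 uses the same level: "performing hypothesis tests at two-sided alpha=.05".

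The opening note of Section 9 says there will be no separate SAP and that this section holds all the analysis plans. Section 9 contains no alpha split, no Holm, Hochberg or Bonferroni step, no hierarchy, and no statement that one or both endpoints must be significant.

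**The concern.** Two tests at .05 give two chances of a false positive. If the trial may claim a causal "role of estradiol in clinically significant symptoms of anxiety and anhedonia" on the strength of either scale, .05 describes the error of each test but not of that claim. Because Section 9 is the whole plan, the missing rule cannot be sitting in another document. Settling it after unblinding would invite the criticism that the choice followed the results.

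**Working it through.** **Inputs from the documents.** Two primary endpoints (1.1, 9.1, 9.4.2); two-sided alpha .05 for each (9.2, 9.4.1); N = 120, effect size f = .15, correlation among repeated measures above .25, repeated-measures ANOVA with within-between interaction, 15% withdrawal, 138 women (9.2); 60 per arm (4.2, 6.3); two groups and four assessments.

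**Assumed.** The correlation r between the two endpoints' test statistics, taken from 0 to .9; one treatment-by-time test per endpoint; either result sufficient for the claim.

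**1. Reproduce the plan's power.** With k = 2 groups and m = 4 times, λ = f²·N·m/(1 − ρ) = .0225 × 120 × 4/.75 = 14.4, with df (k − 1)(m − 1) = 3 and (N − k)(m − 1) = 354. The noncentral F at alpha .05 gives 90.2%, which matches the stated figure of more than 90%. The stated power is therefore for one endpoint at an unadjusted .05.

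**2. Chance of at least one false positive.** This is .05 + .05 − P(both false positive). For independent tests it is 1 − .95² = 9.75%. For correlated tests, the 1-df figures come from the bivariate normal and the 3-df figures from 2 million simulated pairs of chi-square tests:

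| r between tests | 1-df test | 3-df test |
|---|---|---|
| 0 | 9.75% | 9.75% |
| .3 | 9.5% | 9.6% |
| .5 | 9.1% | 9.2% |
| .7 | 8.35% | 8.5% |
| .8 | 7.8% | 8.0% |
| .9 | 7.0% | 7.2% |

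**3. Error if both must be significant.** P(both false positive) cannot exceed either single-test error, so it is at most 5%.

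**4. Error after control.** At .025 each, with independent tests, 1 − .975² = 4.94%; under any correlation it is at most 5%.

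**5. Power for one endpoint**, same formula, f = .15:

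| Analysed | ρ | λ | Alpha .05 | Alpha .025 |
|---|---|---|---|---|
| 102 | .25 | 12.24 | 84.3% | 76.6% |
| 120 | .25 | 14.40 | 90.2% | 84.4% |
| 138 | .25 | 16.56 | 94.0% | 89.9% |
| 120 | .50 | 21.60 | 98.2% | 96.6% |

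The 102 row is 120 × .85: 60 per arm randomized, less the plan's own 15% withdrawal. The 138 row applies only if all 138 are analysed. The .025 column is what applies when only one scale responds.

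**The case against.** The best counter-argument is that these are two separate questions. The synopsis numbers two objectives, 9.1 gives two pairs of hypotheses, and 2.1 treats threat reactivity and approach motivation as distinct constructs. On that reading each claim carries its own 5% error, and joint control is a matter of choice. This stands as a possible intention. But Section 3 merges the two into one causal objective, and nothing says that the claims are separate and need no joint control.

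Second, the central hypothesis in 4.1 speaks of anxiety and anhedonia together, so both might be required. Then no adjustment is needed. That wording is a scientific expectation, however, not a decision rule. If it were the rule, the power of more than 90% in 9.2 would not describe it: at 120 analysed, the chance that both tests succeed runs from about 81% (.902 × .902, independent) up to 90.2% (perfectly correlated).

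Third, the protocol says repeatedly that this is not a clinical efficacy trial. That lowers the stakes of an error but does not remove the issue: 9.1 calls these primary efficacy endpoints, the power is computed for them, and the goal in Section 3 is a causal conclusion.

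A reader might infer that the plan lets either scale alone make the trial positive, so that its error rate simply is 8–10%. The documents do not support that. They define no trial-level success, and the figure depends on an unstated rule and an unstated correlation; above about .8 it falls below 8%.

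**Conclusion.** The point holds in conditional form. As written, STAI and SHAPS are each tested at two-sided .05 and nothing controls the two together. If either can support the Section 3 claim, the chance of at least one false positive primary result lies between about 7% (correlation .9) and 9.75% (independent tests), against a nominal 5%. This assumes one treatment-by-time test per endpoint and a correlation that the documents do not supply.

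Two further inferences should be resisted. The drop from 90.2% to 84.4% is not an upper limit on the cost of control: the loss is 7.7 points at 102 analysed and under 2 points at correlation .5 with 120 analysed. And nothing here bears on how the secondary endpoints should be labelled. The trial is not invalidated; this should be settled before unblinding.

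**What to change.** - **9.4.1:** state that the STAI and SHAPS treatment-by-time tests are controlled together at two-sided .05 by Holm or Hochberg. With two tests, Holm requires the smaller p-value to be at most .025 and then tests the larger at .05. Hochberg declares both significant if both are at most .05, and otherwise requires the smaller to be at most .025.
- **1.1 and Section 3:** reconcile the two-objective and one-objective wording. If the sponsor instead intends that both must be significant, or that these are two separate claims, the text should say so, because the need for adjustment turns on it.
- **9.2:** give power at .025 beside the current figure, stating the number analysed and the correlation assumed, as in the last table under the working.

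The cost is a few sentences and a lower quoted power for a single endpoint. No extra participants or assessments are needed to adopt the rule. Holding 90% for one endpoint at .025 would take about 140 analysed at correlation .25. Under Hochberg nothing is lost when both endpoints reach .05.

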8.2 SAFETY AND OTHER ASSESSMENTS

Safety Screening prior to randomization:

- **Physical examination:** height and weight will be measured to determine eligibility based on BMI. Gynecological exam by Investigator gynecologist will determine if subjects have any signs or history of endometrial disorder, abnormal uterine anatomy, or abnormal ovarian anatomy (confirmed by endometrial ultrasound and/or biopsy).
- **Vital signs** Three stethoscopic blood pressure readings will be measured at enrollment to rule out hypertension.
- **Radiographic assessments.** Subjects will be required to have normal results from a screening mammogram within 12 months prior to enrollment.

The Snaith-Hamilton Pleasure Scale (SHAPS): ¹⁰⁴ assesses anhedonia. SHAPS scores range from 14-56, with higher scores corresponding to higher levels of anhedonia. This scale has shown adequate overall psychometric properties in clinical and student samples ¹⁰⁵. The SHAPS has satisfactory test-retest validity in healthy participants (intraclass correlation coefficient = 0.70, p < 0.001 ¹⁰⁶).

The State-Trait Anxiety Inventory (STAI): the state measure of anxiety from the STAI consists of items such as "I am worried" or "I feel calm" and participants complete the items as to how they currently feel. A higher score indicates higher anxiety. While there are no standard clinical cut-offs for the STAI, past research indicates scores ≥ 40 are clinically significant. ^{107,108} The scale has good median alpha reliability (.92). ¹⁰⁹

Dot-probe (DP) task (15 min): will measure attentional bias to threat (threat responsivity)¹¹⁹. An angry and a neutral face of the same individual are presented vertically simultaneously (trials with neutral faces are controls). Immediately following the face pair, a probe letter replaces either the angry face (threat congruent trial) or the neutral face (threat incongruent trial). Participants indicate the probe letter via button press. The task consists of 144 trials (48 threat congruent, 48 threat incongruent, 48 neutral). Trials are separated by a variable length inter-stimulus interval (900 - 1300 ms). Bias scores are calculated by subtracting the reaction time on threat congruent from threat incongruent trials. Positive scores reflect a bias towards threat and negative scores reflect a bias away from threat. Attention bias calculations exclude trials with incorrect responses, trials with reaction times <150 ms or >2000 ms or >2.5 SD outside the mean.

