9 STATISTICAL CONSIDERATIONS

NOTE: There will not be a formal Statistical Analysis Plan (SAP) attached to this protocol. Rather, details on all analysis plans are to be found in this section under the specific subheadings. We will test whether there are any differences between related population means (time effect, within-subject) and whether mean levels change across time based on the treatment group the participants were randomized to (time x treatment effect, within and between-subject).

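### 9.4.1: each arm keeps its own pre-randomisation week 8 mean, which costs precision; the fixed auto-regressive covariance can also misstate the SE of changes from week 8

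*Combined protocol and SAP*

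**What the plan says.** The protocol has no separate SAP, so section 9 is the whole specification. It plans to test for "any differences between related population means (time effect, within-subject") and for a time-by-treatment effect. 9.4.1 describes a two-way repeated-measures model in PROC MIXED for "mean value change in the primary and secondary outcomes from week 8 to weeks 16, 20, and 24 (within-subject analyses") and by arm. For both primary scores, 9.4.2 has the values "treated as a repeated measure (assessed at weeks 8, 16, 20, and 24"), so week 8 is one of the four responses. Sections 1.2 and 8.3.9 place the week 8 session before randomisation. No baseline covariate or common week 8 mean is stated; 9.4.5 only compares the arms at week 8 by t-test.

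On covariance, 9.4.1 states: "All models will use an auto-regressive covariance structure to account for the repeated assessments of primary and secondary outcomes in the same participants". It gives no order, SAS TYPE= option, spatial version, robust SE or fallback, and its list of diagnostics does not include the covariance structure. 9.2 sizes the trial with "a correlation of >.25 among repeated measures", a single value.

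In 9.1 the alternative for each primary and secondary outcome is that the mean "will significantly change from baseline (week 8) to weeks 16, 20, and 24 in those randomized to active treatment", but not under placebo.

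**The concern.** Two separate matters arise.

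First, at week 8 the arms differ only by chance. A model with a free week 8 mean in each arm subtracts that chance difference in full. A model with one week 8 mean subtracts only the part that the correlation supports. The first is valid, but it carries avoidable noise into every treatment contrast.

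Second, an AR(1) by visit order forces the correlation to fall with the number of visits apart and treats the 8-week gap like the 4-week gaps. If the true pattern differs, the model's SE for a change from week 8 is wrong. Because 9.1 predicts change in one arm and none in the other, a wrong SE at one visit could make that visit's change significant too often or too rarely.

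**Working it through.** **Inputs.** N=120, 60 per arm (9.2, 6.3); four visits at weeks 8, 16, 20 and 24; f=.15, two-sided alpha .05 and correlation .25 (9.2). Correlations up to .70 are tried because of one figure in 8.2: "The SHAPS has satisfactory test-retest validity in healthy participants (intraclass correlation coefficient = 0.70"). Using it as a between-visit correlation is an assumption. Outcomes are scaled to SD 1.

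**1. The plan's own figure.** For the within-between interaction, lambda = f² × N × m/(1−r) = .0225 × 120 × 4/.75 = 14.4. With 3 and 354 df, power is 90.2%. The stated >90% reproduces.

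**2. Common week 8 mean, one visit.** The variance of the arm difference in change is proportional to 2(1−r) with week 8 free and to 1−r² with a common mean. The ratio is (1+r)/2:

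- r=.25: 0.63
- r=.50: 0.75
- r=.70: 0.85

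**3. Common week 8 mean, joint 3-df test, constant correlation .25.** An equal effect d at all three visits has noncentrality 22.5d²/(1−r) = 30d² with week 8 free. With a common mean it is 90d²/[(1−r)(1+3r)] = 90d²/1.3125 = 68.6d². Setting 30d² = 14.4 gives d = 0.69, the equal effect that f=.15 implies. For an effect at one visit only, 30d² rises only to 34.3d². The gain therefore depends strongly on the pattern of the effect.

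**4. SE of change from week 8 under AR(1) by visit order.** In large samples with equal variances, the fitted lag-one correlation is close to the mean of the three adjacent correlations.

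- Constant correlation r: the model variance of change at weeks 16/20/24 is 2(1−r), 2(1−r²), 2(1−r³), against a true 2(1−r). At .25 the SE ratios are 1.00, √(1.875/1.5) = 1.12 and √(1.969/1.5) = 1.15. At .70 they are 1.00, 1.30 and 1.48.
- Calendar decay with 4-week correlation .5 (assumed): adjacent correlations are .25, .5, .5 and the fitted value is .417. The week 16 ratio is √(1.166/1.5) = 0.88. At .8 the fitted value is .747 and the ratio 0.84.

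Per-visit type I error is 2[1−Φ(1.96 × ratio)]: 2.5% (.25) and 0.4% (.70) at week 24 under constant correlation; 8.4% (.5) to 10.0% (.8) at week 16 under decay. A spatial power form does not cure the constant case: its ratios are 1.11/1.14/1.15 at .25 and 1.23/1.41/1.53 at .70.

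The joint test has size of about 4% to 6% under all these patterns. SEs of the LS means are essentially unchanged (ratio at most 1.006).

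**5. Joint-test power (%) at N=120, assumed d=0.4 SD, complete data.** AR(1) columns are simulated, to be read to within about 2 points.

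| True correlation, effect pattern | As written | Common mean only | Unstructured only | Both |
|---|---|---|---|---|
| Constant .25, equal | 33 | 79 | 41 | 78 |
| Constant .50, equal | 45 | 75 | 59 | 81 |
| Constant .70, equal | 66 | 82 | 83 | 91 |
| Constant .25, growing | 21 | 50 | 31 | 52 |
| Constant .70, growing | 30 | 50 | 69 | 76 |
| Constant .25, week 24 only | 33 | 44 | 41 | 46 |
| Constant .70, week 24 only | 68 | 73 | 83 | 84 |
| Constant .25, week 16 only | 40 | 48 | 41 | 46 |
| Constant .70, week 16 only | 86 | 87 | 83 | 84 |
| Decay .5, equal | 40 | 72 | 33 | 65 |
| Decay .7, equal | 55 | 72 | 43 | 63 |
| Decay .8, equal | 69 | 80 | 57 | 70 |

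The common mean never lowers power here. The unstructured form gains in most constant-correlation rows and loses under decay with an equal effect: 7 to 12 points with week 8 free, 7 to 10 with the common mean.

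**6. At the plan's own effect** (f=.15, constant .25), unstructured gains about 4 to 10 points over AR(1) for equal, growing and week-24-only effects, and nothing for a week-16-only effect.

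**The case against.** The strongest reply is that the tests the plan names are sound. Section 9 specifies time and time-by-treatment effects, 9.2 sizes the interaction, and 9.4.2 repeats time and treatment for anxiety and treatment by week for anhedonia. The joint test keeps its size, and no section defines a visit-by-visit test from week 8. A reader might infer from the 8.4% to 10.0% figures that the primary analysis has an inflated false-positive rate. The documents do not support that. Those rates belong to single-visit changes, which 9.1 and 9.4.1 word as hypotheses but do not define as tests, under a decay pattern that the documents do not give. Under the constant correlation of 9.2 the visit-wise error is conservative.

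The reply is also right that d=0.4 is smaller than the planned effect, so the table overstates the covariance gain at f=.15, and that unstructured is a trade-off.

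On missing values the plan says: "Missing data will not be imputed, as the statistical procedures we will apply (proc mixed) are robust to randomly distributed missing data". With withdrawal the covariance also affects the estimates, but little. With 15% withdrawal in one arm related to the last score (an assumed mechanism), AR(1) shifts the week 24 mean of that arm by 0.025 to 0.036 SD, and unstructured by 0.001 SD.

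What stands is the avoidable loss of precision at week 8, and the possible error in the SE of a change that 9.1 words as its hypothesis.

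**Conclusion.** The main point is a free improvement: a common week 8 mean cuts the single-visit contrast variance by 37%, 25% or 15% at correlations .25, .50 and .70. The secondary point is a cheap improvement: the SE of a change from week 8 may be 12% to 48% too large or 12% to 16% too small, depending on a correlation pattern that the documents do not give.

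Two stronger readings do not hold. A reader might infer that the treatment estimate is biased or ignores baseline. It does not: week 8 is a response, so treatment by week already subtracts it, and the unadjusted change is unbiased. A reader might also infer that N=120 or >90% power is wrong. Both reproduce for the repeated-measures ANOVA that 9.2 names.

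The sizes rest on equal variances, the correlations and calendar decay tried, the effect patterns and d=0.4; of these only the .25 is a planning value in the documents. Winsorising at 2 SD was not simulated.

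**What to change.** In 9.4.1 to 9.4.3:

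- Keep week 8 as a response, and enter treatment-by-week terms only for weeks 16, 20 and 24, so that the arms share one week 8 mean. Keep the joint 3-df test and report visit-specific estimates. The time effect of section 9 and the within-arm changes of 9.1 remain estimable.
- Replace the auto-regressive structure with an unstructured covariance and Kenward-Roger degrees of freedom. Name a fallback for non-convergence, for example a random intercept plus spatial power on actual weeks.
- State whether changes from week 8 are tested by visit or only jointly.

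The cost is protocol wording and a few lines of SAS, with no new data. The covariance has 10 parameters instead of 2, which about 120 women can support. The price in power is the loss under calendar decay with an equal effect shown above; both changes together still give 65/63/70% against 40/55/69% as written. The gain is small for a single-visit effect, and for week 16 only at correlation .70 power falls from 86% to 84%. The choice should be fixed before unblinding.
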